5.5 APPENDIX 5 SAMPLE SAS CODE

The multiple imputation and analysis model for the primary analysis approach will be built with the following sample SAS code.

1. 40 datasets with a monotone missing pattern will be obtained, induced by Markov Chain Monte Carlo (MCMC) method on participants who have not taken selected prohibited medications and/or rescue medications or have not discontinued study intervention due to lack of efficacy prior to Week 24.

```
proc mi data=dat_etd seed=16461 nimpute=40 out=dat_mc;  
    mcmc impute=monotone;  
    var angiobl region trt01p iss7bl chg1iss ... chg24iss;  
run;
```

2. For each of the imputed dataset with monotone missing pattern in step 1, the remaining missing data will be imputed using the regression method for the monotone pattern with adjustment for covariates including intervention groups, region, angioedema status at baseline and baseline value of the response variable.

```
proc mi data=dat_mc nimpute=1 seed=16461 out=dat_mi;  
    by _imputation_;  
    class angiobl region trt01p;  
    monotone method=reg;  
    var angiobl region trt01p iss7bl chg1iss ... chg24iss;  
run;
```

3. Each of the 40 imputed datasets will be merged with the one dataset imputed by WOCF approach, and then be analyzed using the main statistical model. These 40 imputed datasets will be saved.

```
%macro w1;  
    %do i=1%to 40;  
        data wocf&i.;  
        set wocf;  
        _imputation_=&i.;  
        run;  
    %end;  
    data wocf_all;  
    set %do j=1 %to 40; wocf&j. %end;;  
    run;  
%mend w1;  
  
%w1  
  
data dat_imp;  
    set dat_mi wocf_all;  
Run;  
  
proc sort data=dat_imp;  
    by _imputation_;  
run;
```

```
proc glm data= dat_imp;
  by _imputation_;
  class region angiobl trt01p;
  model chg24iss = iss7bl angiobl region trt01p;
  lsmeans trt01p / stderr;
  estimate 'Diff Dupilumab vs Placebo' trt01p -1 1;
  ods output LSMeans=implsmeans Estimates=implsmeandiff;
run;
```

4. Applying Rubin's rule to combine analysis results (point estimates and standard errors) from 40 imputations using PROC MIANALYZE for the LS means and difference in LS means between dupilumab and placebo. Sample code:

```
proc sort data=implsMeans; by trt01pn _imputation_; run;

proc mianalyze data= implsmeans;
  by trt01pn;
  modeleffects lsmean;
  stderr stderr;
  ods output ParameterEstimates=lsmeans;
run;

proc mianalyze data=implsmeandiff;
  modeleffects estimate;
  stderr stderr;
  ods output ParameterEstimates=lsmeandiff;
run;
```

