of IL-4/IL-13 by dupilumab represents a novel therapeutic approach for CSU patients. In a small case series of patients who had concurrent AD and CSU and were resistant to omalizumab, treatment with dupilumab improved their urticaria. This further supports the rationale to target aberrant IL-4/IL-13 signaling with dupilumab in patients with CSU. As this is a novel therapy that acts further upstream than IgE-targeted therapies, the clinical trials proposed here will test the efficacy of dupilumab in patients who have failed anti-histamines alone or who have failed both anti-histamines and omalizumab. Efficacy in patients who were intolerant to omalizumab will also be assessed. The master protocol EFC16461 will include 3 studies in CSU patients who remain symptomatic despite the use of H1-AH treatment - 2 studies will be in patients who are omalizumab naïve (Study A and Study C) and the third study in patients who are intolerant or incomplete responders to omalizumab (Study B). The selected dosing regimen is dupilumab 300 mg every 2 weeks (q2w) with a loading dose of 600 mg for adults; 300 mg q2w with a loading dose of 600 mg for adolescents  $\geq$ 60 kg at screening OR 200 mg q2w with a loading dose of 400 mg for adolescents <60 kg at screening; and 200 mg q2w with a loading dose of 400 mg for children  $\geq$ 6 to <12 years of age with weight  $\geq$ 30 kg at screening OR 300 mg q4w with a loading dose of 600 mg for children  $\geq$ 6 to <12 years of age with weight <30 kg and  $\geq$ 15 kg at screening. This dose is expected to achieve concentrations in serum that saturate the IL-4/IL-13 receptor and hence it is expected to provide the maximum benefit and therefore to achieve the optimal benefit/risk ratio in this patient population.

LIBERTY-CSU CUPID Study A was completed and demonstrated that dupilumab at the above-mentioned dosing regimen is efficacious versus placebo in participants with CSU who remain symptomatic despite the use of H1 antihistamine (H1-AH) treatment (6). The trial included a total of 138 participants (132 adults, 4 adolescents and 2 children), with 68 participants in the placebo group and 70 participants in the dupilumab group.

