**Table 1 - Summary of the primary endpoints in Study A - ITT population**

Parameter	Placebo a (N=68)	Dupilumab a (N=70)	Difference (95% CI) b for Dupilumab vs. Placebo	P-value
Primary endpoint for US and US ref. countries (key secondary endpoint for EU and EU ref countries)				
Change from baseline in ISS7 at Week 24	-6.01 (0.94)	-10.24 (0.91)	-4.23 (-6.63, -1.84)	0.0005
Primary endpoint for EU and EU ref. countries (key secondary endpoint for US and US ref countries)				
Change from baseline in UAS7 at Week 24	-12.00 (1.81)	-20.53 (1.76)	-8.53 (-13.16, -3.90)	0.0003

a Values presented are LS mean change from baseline

b Difference is LS mean difference

In regard to the safety endpoints, overall treatment-emergent adverse events reported in at least 5% of participants in any treatment group were comparable for placebo and dupilumab. A total of 58.8% of participants in the placebo group experienced any treatment-emergent adverse event, whereas 54.3% of participants in the dupilumab group experienced any treatment-emergent adverse event. Among the reported treatment-emergent adverse events, skin and subcutaneous tissue disorders were reported in 26.5% of participants in the placebo group and 14.3% of participants in the dupilumab group. These disorders included CSU in 8.8% of participants in the placebo group and 4.3% of participants in the dupilumab group. Additionally, 5 participants (7.4%) of the placebo group versus 1 participant (1.4%) of the dupilumab group experienced angioedema. The trial demonstrated safety results similar to the known safety profile of dupilumab in its approved indications.

Overall, in Study A dupilumab demonstrated clinically and statistically significant efficacy in patients with CSU who remain symptomatic despite the use of H1-AH treatment, as demonstrated by significantly reduced itch and hive severity and urticaria activity compared with standard of care H1-antihistamines alone. Dupilumab was well tolerated and demonstrated an acceptable safety profile in patients with CSU.

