5.3 APPENDIX 3 DEMOGRAPHICS AND BASELINE CHARACTERISTICS, PRIOR OR CONCOMITANT MEDICATIONS

Demographics, baseline characteristics, medical surgical history

The following demographics and baseline characteristics, medical and surgical history and disease characteristics at baseline will be summarized using descriptive statistics in the randomized population.

Demographic variables are

- Age in years (quantitative and qualitative variable: <12, 12- <18, 18- <40, 40 - <65, 65 - <75 and \geq 75 years),
- Gender (Male, Female),
- Race (White, Black or African American, Asian, American Indian or Alaska Native, Native Hawaiian or other Pacific Island, unknown),
- Ethnicity (Hispanic or Latino, Not Hispanic or Latino, Unknown)
- Region (**Asia**: China, Japan; **Latin America**: Argentina; **Western Countries**: Canada, USA, France, Germany, Spain, United Kingdom, **East Europe**: Hungary, Russia)
- Territory (**North America**: Canada, USA; **European Union and UK**: France, Germany, Spain, United Kingdom, Hungary; **Rest of World**: China, Japan, Argentina, Russia)
- Weight in kg (quantitative and qualitative variable: <60, \geq 60 kg)
- BMI in kg/m² (quantitative and qualitative variable: <30, \geq 30 kg/m²)

Baseline safety and efficacy parameters (apart from those listed above) will be presented along with the safety and efficacy summaries.

Medical (or surgical) history includes all the relevant medical (or surgical) history during the lifetime of the participant.

This information will be coded using the version of MedDRA currently in effect at Sanofi at the time of database lock.

Comorbidity will be summarized separately. The following comorbid diseases will be summarized from electronic case report form (eCRF) pages which were filled in by investigators based on participant reporting. Angioedema history will be further summarized under disease characteristics at baseline.

CSU history (Yes, Ongoing condition)

Angioedema (Yes, Ongoing condition)

Atopic Dermatitis (Yes, Ongoing condition)

Allergic rhinitis (Yes, Ongoing condition)

Allergic Conjunctivitis (Yes, Ongoing condition)

Asthma (Yes, Ongoing condition)

Food allergy (Yes, Ongoing condition)

Chronic Rhinosinusitis (Yes, Ongoing condition)

Nasal Polyps (Yes, Ongoing condition)

Eosinophilic Esophagitis (Yes, Ongoing condition)

Disease characteristics at baseline

The following baseline disease characteristics will be summarized by intervention group:

- Age at onset of CSU (years)

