5.5 APPENDIX 5 SAMPLE SAS CODE

The multiple imputation and analysis model for the primary analysis approach will be built with the following sample SAS code.

1. 40 datasets with a monotone missing pattern will be obtained, induced by Markov Chain Monte Carlo (MCMC) method on participants who have not taken selected prohibited medications and/or rescue medications or have not discontinued study intervention due to lack of efficacy prior to Week 24.

A large rectangular area of the page is completely blacked out, representing a redaction of the SAS code for the first step.

2. For each of the imputed dataset with monotone missing pattern in step 1, the remaining missing data will be imputed using the regression method for the monotone pattern with adjustment for covariates including intervention groups, region, angioedema status at baseline and baseline value of the response variable.

[figure not shown]
A large rectangular area of the page is completely blacked out, representing a redaction of the SAS code for the second step.

3. Each of the 40 imputed datasets will be merged with the one dataset imputed by WOCF approach, and then be analyzed using the main statistical model. These 40 imputed datasets will be saved.

A large rectangular area of the page is completely blacked out, representing a redaction of the SAS code for the third step.

4. Applying Rubin's rule to combine analysis results (point estimates and standard errors) from 40 imputations using PROC MIANALYZE for the LS means and difference in LS means between dupilumab and placebo. Sample code:

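### The Study A and B pooling code gives PROC MIANALYZE no complete-data degrees of freedom, so CIs and p-values are slightly too favourable; Study C should confirm or add EDF=

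*SAP*

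**What the plan says.** Section 5.5 of the Study A SAP sets out the primary analysis in four steps. Forty imputed datasets are generated ("proc mi data=dat_etd seed=16461 nimpute=40 out=dat_mc"). Each is fitted in PROC GLM with "model chg24iss = iss7bl angiobl region trt01p". The results are then pooled: "Applying Rubin's rule to combine analysis results (point estimates and standard errors) from 40 imputations using PROC MIANALYZE". The call for the treatment difference is "proc mianalyze data=implsmeandiff", followed only by a modeleffects statement and a stderr statement. The Study B SAP has the same pooling code. Neither call carries an EDF= option, and neither SAP mentions complete-data or small-sample degrees of freedom. The text says only that inference is combined by Rubin's rule.

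In the Study C SAP the code in section 5.5 is blacked out. The visible sentence describes pooling "from 40 imputations using PROC MIANALYZE for the LS means and difference in LS means", with point estimates and standard errors as the inputs.

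Protocol Table 1 (section 2.1) reports the Study A results obtained under this plan: for ISS7 a difference of -4.23, 95% CI -6.63 to -1.84, p = 0.0005; for UAS7 a difference of -8.53, 95% CI -13.16 to -3.90, p = 0.0003.

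**The concern.** An analysis of covariance with N participants and seven parameters has N-7 error degrees of freedom. Imputing part of the data cannot add to them. Rubin's large-sample formula takes no account of this limit. With 40 imputations and modest missing information it returns thousands of degrees of freedom, so the pooled test becomes in effect a normal test. The Barnard-Rubin adjustment corrects this, but PROC MIANALYZE needs the complete-data df through EDF= to apply it. Without it, CIs are too narrow and p-values too small, always in the direction that favours significance.

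The same pooling step serves the continuous secondary endpoints, the subgroup analyses and the tipping-point analysis, whose stopping rule is itself a p-value threshold. The distortion grows as the analysis set shrinks.

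**Working it through.** **Inputs.** Study A was randomized "with 68 participants in the placebo group and 70 participants in the dupilumab group" (protocol 2.1), so N = 138. Region has four levels in the Study A SAP, section 5.3 (the list begins "Region (Asia: China, Japan; Latin America: Argentina"). The model has 1 intercept + 1 baseline + 1 angioedema + 3 region + 1 treatment = 7 parameters. Error df are 138 - 7 = 131 in Study A, 83 - 7 = 76 at the Study B interim, 108 - 7 = 101 at the Study B final analysis, and 150 - 7 = 143 in Study C as planned. The number of imputations is m = 40. The fraction of missing information γ is not in the documents; 5% and 10% are assumed.

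**Reproducing Table 1.** For a candidate reference t(df): SE = CI half-width / t(0.975, df); T = |difference| / SE; p = 2·P(t(df) > T). The half-widths are (6.63 - 1.84)/2 = 2.395 for ISS7 and (13.16 - 3.90)/2 = 4.63 for UAS7. The ranges allow for two-decimal rounding of every printed figure.

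| Reference | ISS7 p | UAS7 p |
|---|---|---|
| Printed in Table 1 | 0.0005 | 0.0003 |
| Normal | 0.00051-0.00054 | 0.00030-0.00031 |
| t on 131 df | 0.00062-0.00066 | 0.00038-0.00039 |

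The normal reference reproduces both printed values. With t on 131 df the table would print 0.0006 or 0.0007 for ISS7 and 0.0004 for UAS7. The smallest df that fits the printed figures is about 395 for ISS7 and about 205 for UAS7, both above the 138 participants.

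**Degrees of freedom with and without EDF=.** Without it, v = (m-1)(1 + 1/r)², where r = γ/(1-γ), which equals 39/γ². This is 39/0.0025 = 15,600 at γ = 5% and 39/0.01 = 3,900 at γ = 10%. With it, v_obs = [(v0+1)/(v0+3)]·v0·(1-γ) and the adjusted df is 1/(1/v + 1/v_obs). For Study A at 5%: v_obs = (132/134)·131·0.95 = 122.6, and the adjusted df is 121.6. At 10% it is 112.8.

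**Size of the error.** Actual size = 2·P(t on adjusted df > critical value used).

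| Analysis | Error df | Adjusted df (10%, 5%) | Nominal | Actual |
|---|---|---|---|---|
| Study A | 131 | 113, 122 | 0.05 | about 0.052 |
| Study C, if the same call | 143 | 123, 133 | 0.05 | about 0.052 |
| Study B interim | 76 | 66, 70 | 0.021 | about 0.024 |
| Study B final | 101 | 87, 94 | 0.043 | about 0.046 |

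The Study A critical value is 1.960 where 1.980-1.981 is needed, so the CI is about 1% too narrow. At the Study B interim a 95% CI is about 1.7-1.8% too narrow, and an interval at the 0.021 level about 2.3% (2.308 against 2.361-2.365).

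**Study A with the adjusted df.** For ISS7, SE = 2.395/1.960 = 1.222 and the CI is -4.23 ± 1.980 × 1.222, which is -6.65 to -1.81, with p about 0.0007. For UAS7, SE = 4.63/1.960 = 2.362 and the CI is -8.53 ± 1.980 × 2.362, which is -13.21 to -3.85, with p about 0.0004.

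**Smaller sets, as an illustration only.** With 45 to 68 participants and seven parameters (38 to 61 error df), a nominal 0.05 is about 0.055 to 0.059. The two counts are the planned Study C limits for angioedema at baseline. The AAS7 set is defined by baseline AAS7 above 0, and its size is not stated.

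**The case against.** Several points on the other side stand.

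- **Study C is not visible.** EDF= is an option in the code, and that code is redacted. A reader might infer from the matching text that Study C repeats the omission. The documents make that likely but do not show it.
- **Nothing confirmatory turns on it.** Study A stays far below 0.05. Study B stopped for futility, which required p above 0.1 on both ISS7 and UAS7, so a shift at the 0.021 boundary had no consequence and the 0.043 test is moot. In Study C the decision would change only if the near-normal p fell between about 0.048 and 0.050.
- **Table 1 follows the pre-specified plan.** The SAP names Rubin's rule, and the code applies Rubin's standard degrees of freedom. A reader might conclude that the Table 1 results must be withdrawn and replaced. They are the planned output and the conclusion is unaffected, so this does not follow.
- **The sizes are approximate.** They treat the Barnard-Rubin df as exact, assume the missing-information fraction, and ignore that the scores are bounded and partly WOCF values.

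Two further replies do not remove the point. Appendix 5 is labelled sample code, but the Study A results behave as that code does. Pre-specifying Rubin's rule does not make a reference with thousands of degrees of freedom right for a model with 131.

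**Conclusion.** The omission is present in the visible Study A and Study B code, and Study A's published figures show its effect. It is one-directional and small: CIs about 1% too narrow in Study A and about 2% at the Study B interim, with actual size near 0.052 for 0.05 and 0.024 for 0.021. It grows in smaller sets such as AAS7 and the subgroups, whose sizes are not given.

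This rests on all four regions being in the model and, for the size figures, on 5-10% missing information. The default used when EDF= is absent is software behaviour that the documents do not describe. The Table 1 check does not depend on it. For Study B the conclusion rests on the identical code, since no Study B estimates are reported here.

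A reader might infer that Study A's success or Study B's futility outcome is in doubt. Neither is.

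**What to change.** In the Study C analysis program, confirm or add EDF= with the error df from the PROC GLM fits in every PROC MIANALYZE call: LS means and differences, for the primary, secondary, subgroup and sensitivity analyses. Barnard-Rubin df then apply throughout. The df should come from the fit of the set being analysed. Add one sentence to Study C SAP 5.5 saying so.

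Where Study A results are quoted, add the small-sample values (ISS7 CI about -6.65 to -1.81, p about 0.0007; UAS7 CI about -13.21 to -3.85, p about 0.0004) as a footnote or sensitivity result, and leave the pre-specified output in place.

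The cost is one option in the code and one SAP sentence. P-values and CIs become slightly less favourable.

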5.6 APPENDIX 6 SELECTION CRITERIA FOR AE/MEDICATION GROUPINGS

Table 14 - List of PTs or Medications for CMQs/CDGs

| Grouping | Preferred Term/ Medication Code | Preferred Term/ Medication |
|----------------|------------------------------------|------------------------------------|
| Conjunctivitis | 10001257 | Adenoviral conjunctivitis |
| Conjunctivitis | 10010725 | Conjunctival irritation |
| Conjunctivitis | 10010726 | Conjunctival oedema |
| Conjunctivitis | 10010736 | Conjunctival ulcer |
| Conjunctivitis | 10010741 | Conjunctivitis |
| Conjunctivitis | 10010744 | Conjunctivitis allergic |
| Conjunctivitis | 10010745 | Conjunctivitis chlamydial |
| Conjunctivitis | 10010749 | Conjunctivitis gonococcal neonatal |
| Conjunctivitis | 10010754 | Conjunctivitis tuberculous |
| Conjunctivitis | 10010755 | Conjunctivitis viral |
| Conjunctivitis | 10018258 | Giant papillary conjunctivitis |
| Conjunctivitis | 10021629 | Inclusion conjunctivitis |

| Grouping | Preferred Term/ Medication Code | Preferred Term/ Medication |
|------------------------------------|------------------------------------|--|
| Conjunctivitis | 10030861 | Ophthalmia neonatorum |
| Conjunctivitis | 10048908 | Seasonal allergy |
| Conjunctivitis | 10049458 | Herpes simplex virus conjunctivitis neonatal |
| Conjunctivitis | 10051625 | Conjunctival hyperaemia |
| Conjunctivitis | 10053991 | Inclusion conjunctivitis neonatal |
| Conjunctivitis | 10061784 | Conjunctivitis bacterial |
| Conjunctivitis | 10062889 | Pingueculitis |
| Conjunctivitis | 10063669 | Photoelectric conjunctivitis |
| Conjunctivitis | 10067317 | Oculorespiratory syndrome |
| Conjunctivitis | 10067817 | Acute haemorrhagic conjunctivitis |
| Conjunctivitis | 10069166 | Blebitis |
| Conjunctivitis | 10071570 | Ligneous conjunctivitis |
| Conjunctivitis | 10074701 | Noninfective conjunctivitis |
| Conjunctivitis | 10075264 | Oculoglandular syndrome |
| Conjunctivitis | 10080825 | Conjunctivitis fungal |
| Conjunctivitis | 10084034 | Conjunctival suffusion |
| Intravenous immunoglobulin therapy | CAS 8000012671 | IMMUNOGLOBULIN HUMAN NORMAL |
| Intravenous immunoglobulin therapy | CAS 8000050682 | IMMUNOGLOBULIN, PORCINE |
| Intravenous immunoglobulin therapy | CAS 8000056919 | IMMUNOGLOBULIN G HUMAN |
| Intravenous immunoglobulin therapy | CAS 8600000563 | IMMUNOGLOBULINS NOS |
| Intravenous immunoglobulin therapy | CAS 8600001670 | IMMUNOGLOBULIN HUMAN NORMAL SLRA |
| Intravenous immunoglobulin therapy | CAS 8600001671 | IMMUNOGLOBULIN HUMAN NORMAL IFAS |
| Intravenous immunoglobulin therapy | RECNO 900708 | OTHER IMMUNOGLOBULINS |
| Intravenous immunoglobulin therapy | RECNO 900722 | IMMUNE SERA AND IMMUNOGLOBULINS |
| Intravenous immunoglobulin therapy | RECNO 900728 | IMMUNOGLOBULINS |
| Intravenous immunoglobulin therapy | RECNO 900914 | SPECIFIC IMMUNOGLOBULINS |
| Intravenous immunoglobulin therapy | RECNO 901112 | IMMUNOGLOBULINS, NORMAL HUMAN |

Abbreviations: CAS : Chemical Abstract Service Registry Number RECNO : Drug Record Number

| Table 10 - Major statistical changes in protocol amendment(s) | 40 |
| Table 11 - Weekly efficacy assessments from daily e-diary | 45 |
| Table 12 - Time window for safety endpoints | 46 |
| Table 13 - Time window for efficacy variables | 47 |
| Table 14 - Time window for pharmacokinetics/pharmacodynamics variables | 47 |
| Table 15 - List of PTs or Medications for CMQs/CDGs | 50 |

VERSION HISTORY

This Statistical Analysis Plan (SAP) only includes the plan for EFC16461 Study B, which is based on the protocol dated 29 April 2021 (amended protocol 4). A separate SAP is prepared for Study A.

This section summarizes the major changes to the SAP. The SAP history table below gives the timing, rationale, and key details for the major changes to the statistical analysis features in the SAP. It includes the major changes in SAP version 2.0 from the most recent approved protocol (amended protocol 4). The first participant was randomized on 03 March 2020. This SAP is approved before the first interim analysis is conducted.

The major changes to the statistical analysis features from a protocol version to another are to be described under [Appendix 2](#).

Table 1 - Major changes in statistical analysis plan

| SAP Version | Approval Date | Changes | Rationale |
|-------------|---------------|---|---|
| 2 | 07-Dec-2021 | 
Sensitivity analysis adding a delta to the WOCF values added
 
Supplementary analysis using a worst possible score added
 
Added blinded medical review to categorize the medications/procedures that constitute a treatment failure
 
Added summaries and analysis of cumulative number of itch and/or hive-free days
 
Added exposure adjusted AE summaries with risk differences and hazard ratios to select AE summaries
 
Added "Keratitis FDA" to other AE groupings
 
Change "key secondary endpoints" to "secondary endpoints" except for
 
Change from baseline in weekly urticaria activity score (UAS7) at Week 24 (except EU and EU reference countries).
 
Change from baseline in ISS7 at Week 24 (in EU and EU reference countries)
 | 
To check robustness by applying worse scores than WOCF
 
An analysis using worst possible score was requested by a Health Authority
 
In line with Health Authority recommendation, to safeguard unbiased definition of intercurrent events for those medications/procedures that constitute treatment failure
 
This additional analysis adds value to provide a total summary over the entire planned treatment period
 
Per a Health Authority recommendation, to consider potentially different exposure of different patients
 
For consistency with other dupilumab studies
 
This change is proposed to harmonize with regional Health Authority requirements
 |

| SAP Version | Approval Date | Changes | Rationale |
|-------------|---------------|--|---|
| | | Removed week 12 endpoints in hierarchy | Based on the data from study A, the treatment effect of dupilumab continued to improve over time through Week 24, and therefore changes in the hierarchy were updated |
| | | Added interim analysis when the first 83 randomized patients would have completed their Week 24 visit | For an earlier assessment of efficacy or stop for futility in this population |
| | | Revised the number of patients at IA to be 83 and added wording to show the actual number of randomized patients is 108 in total | 108 patients are randomized, compared to the planned 104. To preserve the ratio of number of patients at IA to total sample size at final, and alpha spending at IA 0.021, the sample size of IA is increased from 80 to 83 |

